### **Procedures for Reporting Adverse Events**

Adverse events may be spontaneously reported, obtained through non-leading questioning, or noted during examination of a subject. Adverse events will be recorded from the signing of informed consent through the last dose of study drug. Serious adverse events will be recorded from the signing of informed consent through 30 days after the last dose of study drug.

At each visit, new AEs are recorded sequentially on the Adverse Event log. The AE term will note the diagnosis whenever possible, not the individual signs or symptoms (eg., myocardial infarction will be recorded rather than chest pain, elevated cardiac enzymes, and abnormal ECT). Also recorded are:

- Start and stop date and time
- Whether or not the event is continuing
- Frequency (intermittent, continuous)
- Intensity (mild, moderate, severe)
  - Mild: usually transient, requiring no special treatment and generally not interfering with usual daily activities
  - Moderate: usually ameliorated by simple therapeutic maneuvers and impairs usual activities
  - Severe: requires vigorous therapeutic intervention and interrupts usual activities. Hospitalization may or may not be required.
- Relationship to study drug (not related, related): identify relationship as “related” if a causal relationship between the investigational product and an AE is at least a reasonable possibility (i.e. the relationship cannot be ruled out).
- Whether or not the AE is serious (i.e. an SAE). If identified as an SAE, the AE will be reported as an SAE.
- Actions taken (none, study drug dose interrupted, study drug discontinued, other medication change, non-drug therapy, change in parenteral nutrition or IV fluids).
- Outcome (resolved, severity or frequency increased, ongoing, fatal). An individual AE receives only one outcome.

IRB Study Number: 20170189  
Version Date: June 16, 2021  
PI: [name]

NCT02889393

Adverse events not resolved at the end of treatment will be followed until resolution or until the AE is judged by the investigator to have stabilized.

✓

Laboratory values, blood pressure, ECG evaluations, and clinical findings at the scheduled physical examinations will be reported as AEs if they:

- Are considered clinically significant by the investigator
- Fulfill SAE criteria, and/or
- Cause subject discontinuation from the study

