### **Enrollment within 2 months of signing consent**

Inclusion/Exclusion criteria

Vital signs measurements

Nutritional assessment

3-day average fistula output

Complete questionnaires (see additional documents):

1. ASCQ-Me Short Form v2.0 - Social Functioning Impact
2. ASCQ-Me v2.0 - Sleep Impact Short Form

IRB Study Number: 20170189  
Version Date: June 16, 2021  
PI: [name]

NCT02889393

3. Global Health Scale v1.2
4. PROMIS Scale v1.0 - GI Belly Pain
5. PROMIS Scale v1.0 - GI Diarrhea
6. PROMIS Scale v1.0 - GI Nausea and Vomiting
7. PROMIS SF v2.0 - Ability to Participate

Teaching of self-administration of medication

After study enrollment, the subject will be randomly assigned (by a computerized method, using the site 'www.sealedenvelope.com') to begin teduglutide treatment immediately or to continue standard of care (SOC) treatment. The randomization will be performed by a member of the study that is not involved in the informed consent process, and will be enclosed in sequentially numbered opaque envelopes. The envelopes will be given to the PI prior to the enrollment visit. At study visit 5 (day 56), the subject will then cross-over to the opposite treatment assignment. The half-life of teduglutide is 2-3 hours. During the period the subjects are on the "SOC only" treatment arm, the subjects will be given the option to replace some Study visits with Telephone Calls for their convenience. If study visits overlap due to the time window, either visit may be skipped or completed on the same day. Please see information below, and the Study schema.

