**Study Visit 11, Long-Term Follow-up Visit, 3 months after EOT (-2 weeks/+3 months)**

Monitor severe adverse events (SAE) and adverse events (AE)

Collect Concomitant medication review

Collect Nutritional Assessment

Chemistry Panel (sodium, potassium, chloride, bicarbonate, blood urea nitrogen, creatinine glucose)

Liver Function tests (total bilirubin, direct bilirubin, alkalkine phosphatase, alanine aminotransferase, aspartate aminotransferase, lipase, amylase)

Plasma PK (Pharmacokinetics)

- Processed according to separate "Sample Processing Procedure"

3-day average fistula volume (3 days immediately preceding study visit)

Fistula closure (y/n)

Complete Questionnaires (see additional documents)

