### **Serious Adverse Events**

An event that is serious will be recorded on the Serious Adverse Event log. SAEs will be recorded from the signing of informed consent through 30 days after the last dose of study drug.

The most common adverse events are mild and related to gastrointestinal symptoms such as abdominal pain, nausea, and vomiting. If these occur, they will be noted in the adverse event tracking log and reported to the IRB during Continuing Review.

More serious adverse events and any unexpected adverse events will be recorded as per UM HSRO policies and procedures.

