### **Events Necessitating Withdrawal from Study**

The occurrence of any of the following events may necessitate premature withdrawal of a subject from the study:

- Development of any of the following Inclusion/Exclusion criteria:
  - Significant, active, uncontrolled cardiac, hepatic, or renal dysfunction as defined by the Inclusion/Exclusion criteria
- New diagnosis of inflammatory bowel disease
- Use of any excluded medication
- Pregnancy
- Occurrence of a serious adverse event (SAE) thought to be related to study drug and not alleviated by symptomatic treatment
- Unwillingness to continue in the clinical study
- Death of the subject
- Principal Investigator decision (i.e. subject non-compliance with study procedures)
- Significant AE or medical decision that precludes the subject from adhering to study requirements

Readmission to the hospital for fistula-related complications (ex: cellulitis, intra-abdominal abscess, dehydration, etc.) is common and is likely to occur during the study treatment and follow-up period. Unless one of the above “Events Necessitating Withdrawal” occurs, the subject will remain enrolled in the study during hospitalization.

IRB Study Number: 20170189  
Version Date: June 16, 2021  
PI: [name]

NCT02889393

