	Open-Label Extension (up to 12 additional Study Visits and 12 additional Telephone Calls)		
	Extension Study Visit 1 +/- 1 week	Extension Study Telephone Call 1 to End ± 4 d	Extension Study Visit 2 to End +/- 1 week
Informed Consent	X		
Collect Complete Physical Exam Results A	X		X
Collect vital signs measurements B	X		X
Self-administration of medication and teaching if needed	X	X	X
IP Dispensation and Accountability	X		X
Collect chemistry panel results **	X		X
Collect liver function test results **	X		X
Collect serum pregnancy test (if applicable)	X		X
Monitor SAE/AE C	X	X	X
Collect concomitant medication review	X	X	X
Nutritional assessment D	X	X	X
Approx. average daily fistula output	X	X	X
Questionnaires			X F

A. A complete physical examination during an applicable study visit will include an assessment as per clinical judgement.

B. Vital sign measurements during an applicable study visit will include body temperature, heart rate, respiratory rate, and blood pressure. Height will be obtained at Screening only; weight will be measured at screening and during applicable study visits.

C. Patients will be monitored for non-serious adverse events and serious adverse events from the time when informed consent is obtained at Screening up to and including 30 days for SAEs and through the Long Term Follow Up (Study Visit 11) for AEs.

D. May include adjustment of parenteral nutrition (PN) volume as per pre-defined weaning protocol.

E. IP accountability only at visit 10

F. Questionnaires for the Open-Label Extension Study will only be administered at the End of the study

\* PK = Pharmacokinetics, processed according to separate "Sample Processing Procedure"

\*\* Laboratory test results for the Open-Label Extension Study may be collected every 3 months if completed clinically

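### Section 9 stops adverse event recording at the last dose, which makes the safety window depend on the randomised sequence and contradicts the schedule and footnote C

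*Combined protocol and SAP*

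**What the plan says.** Four parts of the combined protocol and SAP bear on how long events are recorded.

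- **Section 9, Procedures for Reporting Adverse Events.** For AEs: "Adverse events will be recorded from the signing of informed consent through the last dose of study drug". For SAEs: "Serious adverse events will be recorded from the signing of informed consent through 30 days after the last dose of study drug". The next paragraph adds: "At each visit, new AEs are recorded sequentially on the Adverse Event log".
- **Section 9, Serious Adverse Events.** The SAE rule is repeated: "SAEs will be recorded from the signing of informed consent through 30 days after the last dose of study drug".
- **Appendix E, footnote C.** Monitoring starts at consent and runs "up to and including 30 days for SAEs and through the Long Term Follow Up (Study Visit 11) for AEs". The starting point of the 30 days is not given.
- **Section 5 visit lists and the Appendix E schema.** AE and SAE monitoring is listed at every contact from Day 7 to Day 112 and again at Visit 11, without distinction by sequence.

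Section 5 randomises subjects to start teduglutide at once or to continue SOC, and then: "At study visit 5 (day 56), the subject will then cross-over to the opposite treatment assignment". The drug period is 8 weeks. Selected subjects may receive up to 12 further months of drug in an open-label extension, offered at end of treatment or at long-term follow-up.

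**The concern.** A window that closes at the last dose suits a parallel design in which everyone stops drug at the same point. In this cross-over the last dose comes halfway through for one sequence and at the end for the other. If staff follow Section 9, non-serious events in SOC time come only from SOC-first subjects, plus any teduglutide-first subjects who later enter the extension. The safety description would then differ between sequences for a reason unrelated to the drug. If staff follow the schedule, nothing is lost. The plan does not say which applies.

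Safety is the first objective in Section 2. Events in the disputed time are to be expected: Section 9 says that readmission for fistula-related complications "is common and is likely to occur during the study treatment and follow-up period".

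Footnote C does not settle the matter. Its AE rule contradicts Section 9, and its 30-day SAE limit does not fit the SAE monitoring listed at Visit 11.

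**Working it through.** The plan gives no figure to reproduce here; Section 7 states that no sample size or power calculation was done. The check applies each recording rule to each sequence on the protocol's own timeline.

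**Inputs**
- Cross-over Day 56, end of treatment Day 112, drug period 8 weeks = 56 days (Section 5).
- Visit 11: 3 months after end of treatment, window -2 weeks to +3 months (Section 5). Taking 3 months as 91 days (assumption), nominal Day 112 + 91 = 203. The window is 203 - 14 = Day 189 to 203 + 91 = Day 294.
- AE-monitoring contacts: Days 7, 14, ..., 112 (16) plus Visit 11 = 17.
- Post-baseline laboratory panels: Days 28, 56, 84, 112 and Visit 11 = 5.
- Planned sample 10. No allocation ratio is stated, so 5 per sequence is assumed and other splits are shown.

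**Section 9 read literally, no extension**

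| | Teduglutide first | SOC first |
|---|---|---|
| Last dose (nominal) | Day 56 | Day 112 |
| AE window ends | Day 56 | Day 112 |
| SAE window ends (last dose + 30) | Day 86 | Day 142 |
| Contacts after AE window | 9 of 17 | 1 of 17 |
| Contacts after SAE window | 5 of 17 | 1 of 17 |
| Laboratory panels after AE window | 3 of 5 | 1 of 5 |
| SOC days without AE recording | 56 of 56 | 0 of 56 |
| SOC days without SAE recording | 56 - 30 = 26 of 56 | 0 of 56 |

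**SOC patient-days lost across the trial** (total 10 × 56 = 560)
- Schedule governs: 0 for AEs and 0 for SAEs. Footnote C's AE rule also gives 0 for AEs.
- Section 9 governs, 5 teduglutide-first subjects: AEs 5 × 56 = 280 of 560 (50%); SAEs 5 × 26 = 130 of 560 (23.2%).
- Section 9 governs, 3 to 7 teduglutide-first subjects outside the extension: AEs 56 × 3 = 168 to 56 × 7 = 392; SAEs 26 × 3 = 78 to 26 × 7 = 182.
- A teduglutide-first subject who enters the extension contributes 0, because the last dose then falls after Day 112.

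**Footnote C on its own.** If its 30 days run from the last dose, and its AEs are the non-serious events it names separately, SAE follow-up ends before AE follow-up:
- Teduglutide first: 203 - 56 - 30 = 117 days (189 - 86 = 103 to 294 - 86 = 208 across the Visit 11 window).
- SOC first: 203 - 112 - 30 = 61 days (189 - 142 = 47 to 294 - 142 = 152).

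**The case against.** The strongest reply is that one sentence in Section 9 stands against everything else. The visit lists, the schema, footnote C's AE rule and Section 9's own statement about recording at each visit all point past the last dose. Staff who work from the schedule would lose nothing. That is fair, and it is why the lower end of the range is 0. But Section 9 is the protocol's named recording procedure, no precedence is stated, and a monitor could cite either reading.

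A second reply is that staff could not close the AE log at Day 56, because the extension is offered only after both arms are complete and nobody yet knows whether the last dose has passed. This makes the 50% figure less likely in practice. It also shows that the Section 9 rule cannot be applied in real time: whether a SOC period counts would turn on a later judgement of response and reliability.

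Other text softens the picture without removing it:
- Unresolved events and persistently abnormal laboratory results are followed up, but that does not extend the window for new events in general.
- Section 9 says that clinically significant findings at scheduled examinations are reported as AEs, with no last-dose limit in that sentence. Some laboratory findings might be caught this way.
- More serious and unexpected events are also recorded under institutional policies that are not in the documents, so the upper SAE figure may be too high.
- The AE definition speaks of illness detected after study drug administration, which leaves some doubt about new illness in a SOC-first subject before any drug.
- The readmission sentence says more about serious than about non-serious events.

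Finally, teduglutide time is covered under every reading, and Section 7 sets out no AE analysis. This limits the consequence to descriptive reporting.

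**Conclusion.** The concern holds. The passages contradict each other, and the Section 9 rule taken at its word makes the safety window depend on the randomised sequence. The loss of SOC observation time is a range because the governing rule is not stated: 0 to 50% for non-serious AEs and 0 to 23% for SAEs. The upper ends rest on five subjects per sequence, completed 56-day periods, nominal dates, no entry to the extension, and no SAE capture through other routes. Visit windows can move the dates by about a week. The primary efficacy endpoint is not affected. The 117-day and 61-day figures for footnote C depend on two readings of an unclear sentence and are secondary.

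**What to change.** Reconcile the two Section 9 statements and footnote C with the schedule, so that one window applies in both sequences: AEs and SAEs recorded from consent through Visit 11. For extension subjects, also record AEs through the last extension contact, and SAEs through 30 days after the last extension dose. The SAE part is already required by Section 9; the AE part matches the monitoring listed at each extension contact. State that events are reported by treatment at onset, using the start date that Section 9 already collects, so that SOC and teduglutide time can be told apart. A clause making clear that the AE definition also covers SOC time before the first dose could be added at the same time.

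This leaves one difference to state in the report. Observation after the last core-study dose remains longer for teduglutide-first subjects, 203 - 56 = 147 days against 203 - 112 = 91 days. Reporting by treatment at onset keeps that visible.

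The cost is wording in three places and a few more events to log. The main study needs no new contacts. No contact is scheduled after the extension ends, so the 30-day SAE check that Section 9 already requires may need one telephone call per extension subject.

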### **Serious Adverse Events**

An event that is serious will be recorded on the Serious Adverse Event log. SAEs will be recorded from the signing of informed consent through 30 days after the last dose of study drug.

The most common adverse events are mild and related to gastrointestinal symptoms such as abdominal pain, nausea, and vomiting. If these occur, they will be noted in the adverse event tracking log and reported to the IRB during Continuing Review.

More serious adverse events and any unexpected adverse events will be recorded as per UM HSRO policies and procedures.

### **Events Necessitating Withdrawal from Study**

The occurrence of any of the following events may necessitate premature withdrawal of a subject from the study:

- Development of any of the following Inclusion/Exclusion criteria:
  - Significant, active, uncontrolled cardiac, hepatic, or renal dysfunction as defined by the Inclusion/Exclusion criteria
- New diagnosis of inflammatory bowel disease
- Use of any excluded medication
- Pregnancy
- Occurrence of a serious adverse event (SAE) thought to be related to study drug and not alleviated by symptomatic treatment
- Unwillingness to continue in the clinical study
- Death of the subject
- Principal Investigator decision (i.e. subject non-compliance with study procedures)
- Significant AE or medical decision that precludes the subject from adhering to study requirements

Readmission to the hospital for fistula-related complications (ex: cellulitis, intra-abdominal abscess, dehydration, etc.) is common and is likely to occur during the study treatment and follow-up period. Unless one of the above “Events Necessitating Withdrawal” occurs, the subject will remain enrolled in the study during hospitalization.

IRB Study Number: 20170189  
Version Date: June 16, 2021  
PI: [name]

NCT02889393

### **10) Potential Benefits to Subjects**

Based on the encouraging results in studies of teduglutide for patients with short bowel syndrome, we expect a clinically significant decrease in daily ECF volume of about 20% magnitude. This could convert high-output fistulas (>500 mL/day) to medium- (200-500 mL/day) or low-output fistulas (<200 mL/day), significantly simplifying fluid/electrolyte management, allow for liberation from parenteral nutrition, or even resolve low-output fistulas completely. It is reasonable to expect an improvement in quality of life.

### **11) Vulnerable Populations\***

We will not routinely enroll pregnant women, prisoners, children, or cognitively impaired adults.

### **12) Resources Available**

The PI has many years of experience conducting and being trained for clinical research. All study personnel will be trained on the protocol by the investigator or designee and complete CITI training. Those obtaining consent will also have prior experience communicating with patients.

### **13) Prior Approvals**

None

### **14) Recruitment Methods**

#### **Recruitment Procedures**

The Study Staff will perform a daily screen of the inpatient census of the “Surgical Nutrition” team at the University of Miami Hospital as well as the outpatient census of the Surgical Nutrition clinic for adults with ECF. In order to screen for eligible patients, the study team is requesting partial HIPAA waiver. When a patient is found to be eligible, the primary health provider team (usually a physician or nurse practitioner) who is known to the potential subject will be contacted for approval for the patient to be contacted for research purposes. This provider will initially introduce the study to the patient and verbally obtain the patient’s permission to be contacted by study staff. The patient will then be approached for discussion of the trial and informed consent, as outlined in the consent procedures below.

Potential subjects will not be contacted by phone for recruitment. Recruitment will not involve restrictions on sociodemographic factors including gender or ethnic characteristics. Recruitment will be devoid of any procedures which could be construed as coercive. If the potential subject is the Investigator’s own patient, the Investigator will ask a physician colleague to initially explain the study and also recommend that the patient discuss participation with other health care providers. These colleagues will stress that participation is voluntary, that they do not have to participate, and the decision not to participate will not affect their care, now or in the future.

IRB Study Number: 20170189  
Version Date: June 16, 2021  
PI: [name]

NCT02889393

**15) Local Number of Subjects: 10**

**16) Monitoring And Quality Assurance**

Study Staff will maintain the data in an electronic database stored in a secure location on password-protected computer system. The consent forms will be kept in files which will be stored in a secure location. De-identified data will be uploaded to VELOS electronic database. The PI will confirm the completeness of data being entered in the electronic database

In order to protect all subjects' confidentiality, we will store data on a password-protected network. Subjects will receive a study-specific unique identifier and the medical record number (MRN) will be uncoupled from the data. The decoder key for study identifier and MRN will be stored in a separate, password-protected file.

**Trial Monitoring, Auditing, and Inspecting**

The investigator will permit trial-related monitoring, quality audits, and inspections by, government regulatory authorities, of all trial-related documents (e.g., source documents, regulatory documents, data collection instruments, case report forms). The investigator will ensure the capability for inspections of applicable trial-related facilities. The investigator will ensure that the trial monitor or any other compliance or QA reviewer is given access to all trial-related documents and trial-related facilities.

Participation as an investigator in this trial implies the acceptance of potential inspection by government regulatory authorities.

In addition to the Clinical Monitoring component of this protocol, Quality Assurance (QA) to assess compliance with GCP and applicable regulatory requirements. Data or documentation audited shall be assessed for compliance to the protocol, accuracy in relation to source documents and compliance to applicable regulations.

**17) Confidentiality**

The protected health information collected for the purpose of this research study will be assigned a research code number and any obvious patient identifiers (name, social security number, hospital record number) will be removed from this information. Both the confidential health information and the information linking the research code numbers to the patients' identities will be stored in a secure manner (e.g., locked file cabinet, password protected database) accessible only to the research study personnel. The information linking the research code numbers to the patients' identities will be stored separate from the confidential health information.

Clinical data will be collected for no longer than one year after the patient has had the initial surgery. Data will be de-identified and stored on a password-protected network

IRB Study Number: 20170189  
Version Date: June 16, 2021  
PI: [name]

NCT02889393

accessible only to research staff. Data will be retained for at least six years following conclusion of the study on this network.

